### **14 Publication Authorship Requirements**

Authorship for any Otsuka-sponsored publications resulting from the conduct of this trial will be based on International Committee of Medical Journal Editors (ICMJE) authorship criteria (<http://www.icmje.org/recommendations>). According to ICMJE guidelines, one may be considered an author only if the following criteria are met:

- 1) Substantial contributions to the conception or design of the work; or the acquisition, analysis, or interpretation of data for the work; AND
- 2) Drafting the work or revising it critically for important intellectual content; AND
- 3) Final approval of the version to be published; AND
- 4) Agreement to be accountable for all aspects of the work in ensuring that questions related to the accuracy or integrity of any part of the work are appropriately investigated and resolved.

All authors must meet the above criteria, and all who qualify for authorship based on the above criteria should be listed as authors.

Investigators or other trial participants who do not qualify for authorship may be acknowledged in publications resulting from the trial. By agreeing to participate in the trial, investigators or other trial participants consent to such acknowledgement in any publications resulting from its conduct.

10.7.2	DIEPSS, AIMS, and Barnes Akathisia Rating Scale (BARS)	17
10.7.3	Columbia-Suicide Severity Rating Scale (C-SSRS).....	18
11	Pharmacokinetic Analyses	18
12	Pharmacodynamic Analyses.....	18
13	Pharmacogenomic Analyses	18
14	Interim Analysis.....	18
15	Changes in the Planned Analyses.....	19
16	References.....	19
17	History of Amendments	19

List of Appendices

Appendix 1	Criteria for Identifying Vital Signs and Weight of Potential Clinical Relevance	20
Appendix 2	Criteria for Identifying Laboratory Values of Potential Clinical Relevance	21
Appendix 3	Criteria for Identifying ECG Measurements of Potential Clinical Relevance	22
Appendix 4	Adverse Events of Interest.....	23
Appendix 5	List of Summary Tables.....	79
Appendix 6	List of Subject Data Listings.....	83

List of Abbreviations and Definition of Terms

Abbreviation	Definition
AIMS	Abnormal Involuntary Movement Scale
ALP	Alkaline phosphatase
ALT	Alanine aminotransferase
AST	Aspartate aminotransferase
BARS	Barnes Akathisia Rating Scale
BMI	Body mass index
BUN	Blood urea nitrogen
CGI	Clinical Global Impression
CGI-I	Clinical Global Impression - Improvement
CGI-S	Clinical Global Impression - Severity of Illness
CK	Creatine kinase
CPK	Creatine phosphokinase
C-SSRS	Columbia-Suicide Severity Rating Scale
DIEPSS	Drug Induced Extra-Pyramidal Symptoms Scale
DSM-5	Diagnostic and statistical manual of mental disorders fifth edition
EQ-5D-5L	EuroQol-5 Dimension, 5 response level version
GCP	Good Clinical Practice
GOT	Glutamic-oxaloacetic transaminase
GPT	Glutamic-pyruvic transaminase
HAM-D	Hamilton Rating Scale for Depression
HDL	High-density lipoprotein
LDH	Lactate (lactic acid) dehydrogenase
LDL	Low-density lipoprotein
LOCF	Last observation carried forward
MADRS	Montgomery Åsberg Depression Rating Scale
MedDRA	Medical Dictionary for Regulatory Activities
PT	Preferred Term
QTc	QT corrected for heart rate
QTcB	QT corrected for heart rate by Bazett's formula
QTcF	QT corrected for heart rate by Fridericia's formula
QTcN	QT corrected for heart rate by FDA Neuropharmacological Division formula
SDS	Sheehan Disability Scale
SNRI	Serotonin-noradrenaline reuptake inhibitor
SOC	System Organ Class
SSRI	Selective serotonin reuptake inhibitor
TEAE	Treatment-emergent adverse event
γ-GTP	γ-glutamyl transpeptidase

1 Introduction

This statistical analysis plan documents in detail the statistical analysis methods planned for Trial 331-102-00059.

2 Trial Objectives

The objective of the trial is to assess the safety and efficacy of the long-term use of brexpiprazole as adjunctive therapy in concomitant use with a commercially available antidepressant (selective serotonin reuptake inhibitor [SSRI] or serotonin-noradrenaline reuptake inhibitor [SNRI] for rollover subjects and SSRI, SNRI, or mirtazapine for new subjects) in subjects with major depressive disorder who continue receiving the treatment from the double-blind trial (331-102-00058) and in newly enrolled patients 65 years or older with major depressive disorder.

3 Trial Design

3.1 Type/Design of Trial

The trial is a multi-center, open-label trial to assess the safety and efficacy of the long-term use of brexpiprazole as adjunctive therapy in conjunction with a commercially available antidepressant (SSRI or SNRI for rollover subjects and SSRI, SNRI, or mirtazapine for new subjects) at a dose and regimen specified in the package insert.

Subjects of the trial are those who have completed the double-blind period (Phase B) of the double-blind trial (331-102-00058), and newly enrolled patients 65 years or older with major depressive disorder who have received 1 to 3 adequate antidepressant drug treatments^a for major depressive episodes and have shown an inadequate response^b to all of these treatments.

The trial design is shown in Figure 3.1-1. The trial comprises a screening period, treatment period, and post-treatment observation period.

^aDefinition of "adequate antidepressant drug treatment" is provided below.

Treatment with an antidepressant at an approved dose for at least 6 weeks (for combination therapy, treatment for at least 3 weeks)

^bDefinition of "inadequate response" is provided below.

With complete recovery from depressive symptoms and not the slightest improvement considered as 100% and 0%, respectively, patients carry out self-evaluations for improvement by antidepressant drug treatments used to date, from among 4 grades (< 25% Improvement, 25% to 49% Improvement, 50% to < 75% Improvement, and ≥ 75% Improvement), with the evaluations corresponding to < 25% Improvement or 25% to 49% Improvement classified as inadequate response.

Patients who, among 1 to 3 adequate antidepressant drug treatments, have received treatment for ≥ 6 weeks at least once (receiving only combination therapies for ≥ 3 weeks does not qualify) are eligible for selection.

[figure not shown]

Figure 3.1-1 Trial Design

^aAdministration of brexpiprazole will commence at 1 mg/day and the dose will be increased to 2 mg/day after observations, examinations, and assessments at Week 1. Subjects who cannot tolerate doses of 2 mg/day will be withdrawn from the trial.

3.2 Trial Treatments

1) Drugs, dose, and regimen

- Commercially available antidepressant

For rollover subjects, an antidepressant (SSRI or SNRI) used in the double-blind trial (331-102-00058) will continue to be used throughout the treatment period, with no changes from the final dose and regimen. For new subjects, an antidepressant (SSRI, SNRI, or mirtazapine) being used at the time of informed consent will continue to be used throughout the treatment period, with no changes from the dose and regimen used at informed consent.

During the treatment period, dose adjustment within the approved dose range is allowed according to the judgement of the investigator or subinvestigator, but the dose may not be altered at the time of dose escalation of brexpiprazole at Week 1.

- **Brexpiprazole**

Administration of brexpiprazole will commence at 1 mg/day and subjects will continue to receive a single brexpiprazole 1 mg tablet once daily by the oral route until the observations, examinations, and evaluations at Week 1. Following the observations, examinations, and evaluations at Week 1, subjects will be administered a single brexpiprazole 2 mg tablet once daily by the oral route. Subjects who cannot tolerate doses of 2 mg/day will be withdrawn from the trial.

2) Treatment period

52 weeks

3.3 Trial Population

Adult and elderly patients with "major depressive disorder, single episode" or "major depressive disorder, recurrent episode" according to the classification criteria of the *Diagnostic and Statistical Manual of Mental Disorders*, fifth edition (DSM-5)

3.3.1 Number of Subjects and Trial Population

The trial will be conducted in patients who have major depressive disorder (major depressive disorder, single episode; major depressive disorder, recurrent episode) according to the DSM-5 classification. Concerning rollover subjects from the double-blind trial (331-102-00058), their eligibility for proceeding to the long-term trial will be assessed, after acquisition of informed consent to the long-term trial, based on the results of examinations and assessments at Week 6 of the double-blind period (Phase B) of the double-blind trial (331-102-00058) and at baseline. The eligibility of new subjects will be judged after acquisition of informed consent from elderly patients 65 years or older, based on the results of examinations and assessments at screening and baseline. As the sample size needed to assess the safety and efficacy of brexpiprazole in the elderly, the number of subjects receiving the treatment was set at 30.

3.4 Trial Visit Window

For all endpoints, acceptable windows for analysis are specified, and analysis should be based on the analysis time points regardless of time points recorded on the case report form.

Acceptable windows for analysis are shown in Table 3.4-1. Day 1 is defined as the day when treatment with the investigational medicinal product (IMP) begins. If multiple data exist within an acceptable window, the last data within the window will be used in analysis. Data obtained 7 days or later after the final dosing will be excluded from the analysis.

Table 3.4-1	Acceptable Windows for Analysis	
Week	Target Day	Trial Day Interval
Baseline	1	- 1
Week 1	7	2 - 10
Week 2	14	11 - 21
Week 4	28	22 - 42
Week 8	56	43 - 70
Week 12	84	71 - 98
Week 16	112	99 - 126
Week 20	140	127 - 154
Week 24	168	155 - 182
Week 28	196	183 - 210
Week 32	224	211 - 238
Week 36	252	239 - 266
Week 40	280	267 - 294
Week 44	308	295 - 322
Week 48	336	323 - 350
Week 52	364	351 - 385

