- Pregnancies are also defined as IREs. Although normal pregnancy is not an AE, it will mandate IMP discontinuation and must be reported on an IRE form to the sponsor. Pregnancy will only be recorded in the source documents and the AE Section of the CRF if there is an abnormality or complication. This applies both to pregnancies of subjects and pregnancies of subjects' partners.

Clinical Laboratory Assessment Value Changes: It is the investigator's or subinvestigator's responsibility to review the results of all laboratory tests as they become available. This review will be documented by the investigator's or subinvestigator's dated signature on the laboratory report. For each abnormal laboratory test result, the investigator or subinvestigator needs to verify whether this is an abnormal (ie, clinically relevant) change from baseline for that individual subject. This determination, however, does not necessarily need to be made the first time an abnormal value is observed. The investigator or subinvestigator may repeat the laboratory test or request additional tests to verify the results of the original laboratory tests. If this laboratory value is considered medically relevant by the investigator or subinvestigator (subject is symptomatic, requiring corrective treatment or further evaluation), or if the laboratory value leads to discontinuation or meets the criteria for an SAE, this is considered an AE.

Severity: Adverse events will be graded on a 3-point scale and reported. The intensity of an AE is defined as follows:

**1 = Mild:** Discomfort noticed, but no disruption to daily activity.

**2 = Moderate:** Discomfort sufficient to reduce or affect normal daily activity.

**3 = Severe:** Inability to work or perform normal daily activity.

IMP Causality: Assessment of causal relationship between an AE and the IMP:

**Related:** There is a reasonable possibility of a temporal and causal relationship between the IMP and the AE.

**Not related:** There is no temporal or reasonable relationship between the IMP and the AE.

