10.3 Clinical Laboratory Data

For each quantitative laboratory parameter, descriptive statistics of actual measurements and changes from baseline at each time point and the last assessment time point (Week 52 LOCF) will be calculated.

For each quantitative laboratory parameter, actual measurements will be classified as "lower than the lower limit of the reference range," "within the reference range," and "higher than the upper limit of the reference range" using the reference range specified by the central laboratory, and a shift table from baseline will be produced.

For each qualitative laboratory parameter, a shift table from baseline will be produced.

Numbers and proportions of subjects with laboratory test values not meeting the criteria for potentially clinically significant laboratory test values (Appendix 2) at baseline and meeting the criteria after treatment will be determined. A listing of these subjects will be provided.

Numbers and proportions of subjects with postdose values of alanine aminotransferase (ALT), aspartate aminotransferase (AST), and total bilirubin (TBL) meeting Hy's Law criteria (ALT or $AST \geq 3 \times$ the upper limit of normal [ULN] and $TBL \geq 2 \times$ ULN) will be determined. A listing of these subjects will be provided.

Numbers and proportions of subjects with a prolactin value not meeting the criteria of $> 1 \times$ ULN, $> 2 \times$ ULN, or $> 3 \times$ ULN at baseline and meeting the criteria after treatment will be determined by sex. A listing of these subjects will be provided.

Numbers and proportions of subjects with postdose values of fasting low-density lipoprotein (LDL) cholesterol, high-density lipoprotein (HDL) cholesterol, triglyceride, and blood glucose meeting the criteria for changes in glucose and lipid metabolism-

related parameters (Table 10.3-1) will be determined by baseline value. A listing of these subjects will be provided.

Table 10.3-1 Changes in Glucose and Lipid Metabolism-related Parameters		
LAB PARAMETER	BASELINE	ANYTIME POST BASELINE
LDL Cholesterol, Fasting (mg/dL)	Borderline 100-<160 Normal/Borderline <160 Normal <100 Any Value	High >=160 High >=160 Borderline/High >=100 Increased >=30
HDL Cholesterol, Fasting (mg/dL)	Normal >=40 Any Value	Low <40 Decreased >=20

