10.7.3 Columbia-Suicide Severity Rating Scale (C-SSRS)

Numbers and proportions of subjects for each C-SSRS item (suicidality, suicidal ideation, suicidal behavior, completed suicide, emergence of suicidal ideation, emergence of serious suicidal ideation, worsening of suicidal ideation, and emergence of suicidal behavior) at each time point and in the overall period after initiation of IMP treatment (including the post-treatment observation period, at discontinuation, and unscheduled visits) will be determined. A listing of subjects with emergence of suicidal ideation, emergence of serious suicidal ideation, worsening of suicidal ideation, and emergence of suicidal behavior will be provided. Items of suicidal ideation and suicidal behavior will also be summarized in the same manner.

- Suicidality: “Yes” for any item of suicidal ideation or suicidal behavior
- Suicidal ideation: “Yes” for any item of suicidal ideation
- Suicidal behavior: “Yes” for any item of suicidal behavior
- Emergence of suicidal ideation: Change from “No” at baseline to “Yes” after baseline for suicidal ideation
- Emergence of serious suicidal ideation: Change from “No” at baseline to “Yes” with Grade 4 or 5 after baseline for suicidal ideation
- Worsening of suicidal ideation: Increase in the grade of suicidal ideation from baseline
- Emergence of suicidal behavior: Change from “No” at baseline to “Yes” after baseline for suicidal behavior

11 Pharmacokinetic Analyses

Not applicable.

12 Pharmacodynamic Analyses

Not applicable.

13 Pharmacogenomic Analyses

Not applicable.

14 Interim Analysis

None.

15 Changes in the Planned Analyses

- The following changes were made to categorical analyses of QTc:
 - Only subjects with postdose QTc meeting the criteria will be summarized, instead of summarization at all time points.
 - Only subjects with QTc not meeting the criteria at baseline and meeting the criteria after baseline will be summarized.
- C-SSRS will be analyzed in the overall period after initiation of IMP treatment, not at the last assessment time point.

16 References

Not applicable.

17 History of Amendments

Table 17-1 History of Amendments		
Version	Date	Major Changes
1.0	01 Jun 2021	Not applicable

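### SAP 3.4 takes the last value in each window for all endpoints and does not exempt the ever-met-criterion safety tables, so a normal recheck can remove an abnormal laboratory value from those counts

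*SAP*

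**What the plan says.** SAP 3.4 states its scope first: "For all endpoints, acceptable windows for analysis are specified, and analysis should be based on the analysis time points". Records are assigned by trial day, whatever visit label the case report form carries. The selection rule follows: "If multiple data exist within an acceptable window, the last data within the window will be used in analysis". A cut-off is added: "Data obtained 7 days or later after the final dosing will be excluded from the analysis".

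The outlier tables are defined later in the SAP:

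- **Appendix 2 laboratory criteria (10.3).** The sentence describes subjects who were outside the criteria "at baseline and meeting the criteria after treatment will be determined. A listing of these subjects will be provided". Prolactin above 1, 2 and 3 times ULN is worded in the same way.
- **Hy's Law (10.3).** "Numbers and proportions of subjects with postdose values of alanine aminotransferase (ALT), aspartate aminotransferase (AST), and total bilirubin (TBL) meeting Hy's Law criteria" are to be determined.
- **Fasting lipids and glucose (Table 10.3-1).** The post-baseline column is headed "ANYTIME POST BASELINE".
- **QTc and other ECG criteria (10.6), vital signs (10.4) and weight (10.7.1).** These count subjects meeting criteria after treatment or on treatment.

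None of these says whether repeat or unscheduled records are eligible. Two other sections do say which records they use. Section 10.7.3 (C-SSRS) expressly includes the post-treatment observation period and data "at discontinuation, and unscheduled visits". Section 10.7.2 adds the worst postdose value for DIEPSS, AIMS and BARS.

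Protocol 5.1 says that for an abnormal laboratory result the investigator or subinvestigator "may repeat the laboratory test or request additional tests to verify the results of the original laboratory tests".

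**The concern.** A last-in-window rule is harmless for a mean at a visit. It is not neutral for a count of subjects who ever crossed a threshold when the second measurement is taken because the first was abnormal. The recheck then becomes the analysed value. If it is back below threshold, the flagged value leaves the table, and so may the subject. The outlier listings cover the same subjects, so they could miss the case too.

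The trial is sized for safety: about 100 subjects completing 52 weeks and 30 elderly new subjects receiving treatment (SAP section 4). One lost subject is 1/100 = 1 percentage point in the first group and 1/30 = 3.3 points in the second. Two programmers could also read the SAP differently, one applying 3.4 to the outlier tables and one not, and produce different safety tables from the same data.

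**Working it through.** The plan states no figure for this point, so there is none to reproduce. The check has four steps.

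**1. Can a recheck fall in the same window?** Visit days and tolerances come from Protocol Table 3.7.1.6-1 and windows from SAP Table 3.4-1. Laboratory tests and ECGs are scheduled on treatment at Weeks 4, 8, 16, 24, 32, 40 and 52 (Protocol 3.7.4.2 and 3.7.4.4).

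Days left = last day of window − visit day.

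| Week | Permitted visit days | Window | Left, latest visit | Left, on reference day | Left, earliest visit |
|---|---|---|---|---|---|
| 4 | 29 ± 2 = 27–31 | 22–42 | 42 − 31 = 11 | 42 − 29 = 13 | 42 − 27 = 15 |
| 8 | 57 ± 7 = 50–64 | 43–70 | 70 − 64 = 6 | 70 − 57 = 13 | 70 − 50 = 20 |
| 52 | 365 ± 7 = 358–372 | 351–385 | 385 − 372 = 13 | 385 − 365 = 20 | 385 − 358 = 27 |

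Weeks 16, 24, 32 and 40 give the same 6, 13 and 20 days as Week 8. A recheck one to two weeks after a visit will therefore often share its window. At Week 52 the 7-day cut-off can bind first: once dosing has ended, only a recheck within 6 days of the final dose can replace the visit value.

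**2. What does the rule then do?** Take assumed values: ALT 3.4 × ULN on Day 57, 1.2 × ULN on Day 64, and 1.0 × ULN at the other visits. Days 57 and 64 both lie in 43–70, so 3.4 keeps only Day 64 for Week 8. The largest retained value is 1.2, and the subject is not counted under ALT ≥ 3 × ULN. With all postdose values the subject is counted.

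**3. Which way can the count move?** The retained values are a subset of the postdose values. A subject who meets a criterion on the subset also meets it on the full set, so the count from the subset is at most the full count. A late abnormal value may replace an early normal one, but that adds nobody whom the full set would miss.

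**4. How large could the loss be?** The documents do not give the true outlier rate p or the share f of outlier subjects lost, so both are assumed here.

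Expected count = n × p × (1 − f). P(at least one seen) = 1 − [1 − p(1 − f)]^n.

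| n | p | f = 0 | f = 0.25 | f = 0.50 | f = 0.75 |
|---|---|---|---|---|---|
| 100 | 2% | 0.867 | 0.779 | 0.634 | 0.394 |
| 100 | 5% | 0.994 | 0.978 | 0.920 | 0.716 |
| 30 | 2% | 0.455 | 0.365 | 0.260 | 0.140 |
| 30 | 5% | 0.785 | 0.682 | 0.532 | 0.314 |

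At n = 100 and p = 2% the expected count falls from 2.0 to 1.5, 1.0 and 0.5.

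Here f is a share of subjects, not of values. Let r be the share of flagged values overwritten by a normal recheck. A subject with k flagged values is lost only if all k are overwritten, which has probability r^k if they are independent. With r = 0.5 that is 0.5 for k = 1, 0.25 for k = 2 and 0.125 for k = 3. The factor (1 − r) therefore applies only if every affected subject has a single flagged value.

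**The case against.** The best reply is that the specific text governs the general. Section 3.4 maps data to analysis time points, so its natural object is by-visit and Week 52 LOCF statistics. The outlier tables speak of values after treatment, of postdose values or of any time after baseline. SAP section 15 says QTc categories are no longer summarised at each time point. On that reading every postdose value already counts. The reading is plausible and may be what was meant, but the SAP does not state it. Section 3.4 claims all endpoints, and section 15 does not say which record within a window is eligible. So the loss follows from a literal reading and is not demonstrated.

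Several further inferences are tempting but unsupported:

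- **That abnormal ECGs, weights or vital signs are also routinely rechecked away.** Protocol 5.1 foresees repeats only for laboratory tests, and only as an option. An unscheduled ECG, vital-sign or weight value would fall under the same rule, but nothing in the documents leads one to expect many.
- **That the worst postdose value for the rating scales contradicts 3.4.** It can be taken over windowed values, so it does not.
- **That naming unscheduled visits for C-SSRS proves they are excluded elsewhere.** The C-SSRS text also had to override the 7-day cut-off to bring in the post-treatment period. Unscheduled records can enter the windows, because assignment is by day.
- **That the abnormal value disappears from the report.** Combined ALT or AST and bilirubin elevations require an immediately reportable event form and an adverse event entry (Protocol 5.4). Medically relevant laboratory values are adverse events (Protocol 5.1). Full laboratory and ECG listings are planned (SAP Appendix 6).

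It is also true that the trial is uncontrolled and descriptive, with no primary or secondary outcome variable, so no test or between-arm comparison depends on these counts.

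**Conclusion.** The point holds as a gap in the SAP text. As written, 3.4 allows a normal recheck in the same window to displace an abnormal laboratory value from the Appendix 2, Hy's Law and prolactin counts, and the effect can only be downward. For fasting lipids and glucose the fault is a direct conflict between 3.4 and the header of Table 10.3-1, which must be reconciled.

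The size cannot be stated. A value is lost only if it is rechecked, the recheck is in the same window and inside the 7-day cut-off, and the recheck is below threshold. A recheck falling in the next window leaves the first value in place. A subject is lost only if this happens to every flagged value, so persistent elevations remain counted. A reader might infer that incidence falls by the share of values rechecked to normal; that is the upper limit at subject level. The probabilities above rest on assumed rates and show only that small groups are sensitive.

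**What to change.** State in SAP 3.4 that last-in-window selection applies only to by-visit and Week 52 LOCF summaries and to by-visit shift tables. State also that all on-treatment post-baseline values, including repeat and unscheduled ones, enter the outlier tables for laboratory criteria, Hy's Law, prolactin, lipids and glucose, QTc and other ECG criteria, vital signs and weight. This also settles the conflict with Table 10.3-1.

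Leave metabolic syndrome on its present definition. Table 10.3-2 requires central obesity and two of three other criteria at the same visit, and a repeat blood test need not come with a waist or blood pressure measurement.

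The cost is a sentence or two in the SAP, and if this was already the intention the tables do not change. The downside is that outlier counts may be slightly higher and may include unconfirmed or spurious values.
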